3.1 Eligibility

3.1.1 Case Selection Criteria

- 7-12 years old (grade 1 to grade 6 of primary school);
- Spherical Equivalent ranged from - 0.5D to - 6.0D, astigmatism < 0.75D, binocular diopter gap < 1.0D;
- No ophthalmopathy except ametropia was found.

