3.4.2.12 Wide angle OCT/OCTA (Zeiss-9000) Wide-angle OCT/OCTA examinations were performed after cycloplegia. OCT/OCTA location: macular + optic disc area. Shooting mode: 12*12mm, 15*9mm angio mode; 16mm loop sweep mode (horizontal and vertical directions) a total of 8 scans. Shooting requirements: communicate more with the subject; the forehead and chin must be close to the instrument. If the image quality is affected by blinking or eye movement during shooting, participants need to re-shoot. This item is optional for children under 6 years old.

3.4.3 Questionnaire: The questionnaire is about the time children spend on outdoor activities and near work.

4. Follow up

4.1 Frequency: Combined use of 1% atropine and 0.01% atropine group is followed up after first week, then every three months. 0.01% atropine group is followed up every three months.

4.2 Examinations:

4.2.1 First week follow up for combined use group: accommodation, near vision acuity > mesopic pupil size > Autorefraction and subjective refraction > IOL-Master, Pentacam, Swept-source optical coherence tomography (SS-OCT, Topcon), wide-angle optical coherence tomography angiography(OCTA,Zeiss-9000)

4.2.2 Every three months: accommodation, near vision acuity > mesopic pupil size > slit lamp anterior segment examination > cycloplegia > Autorefraction and subjective refraction > IOL-Master, Pentacam, Swept-source optical coherence tomography (SS-OCT, Topcon), wide-angle optical coherence tomography angiography(OCTA,Zeiss-9000)

5. Statistical Analysis

5.1 Descriptive statistics A. Continuity variables: sample size, mean, standard deviation, minimum, maximum, quartile B. Classification variable or grade variable: frequency distribution

5.2 statistical methods A. Continuous variables: The normality test uses the Kolmogorov-Smirnov test. If the normal distribution is satisfied, the t test or one-way ANOVA is used; if the normal distribution is not satisfied, the Mann-Whitney U test or the Kruskal Wallis test is used. The two-two comparison between groups was performed using the Bonferroni method. B. Categorical variable: chi-square test. C. Correlation analysis:

simple linear regression and stepwise multiple linear regression, using nonlinear regression if necessary.

5.3 Statistical significance All differences were statistically defined as $P < 0.05$ (bilateral)

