5.4 Subgroup analysis Subjects will be assigned to different subgroups for subgroup analysis based on age, gender, diopter, axial length, fundus structure, and functional changes.

5.5 Interim analysis Baseline data (2019) and follow-up data are used for analysis and reporting.

6. Ethical issues

6.1 Ethics committee The study will be carried out after the approval of the Shanghai General Hospital Ethics Committee and strictly abide by the Helsinki Declaration.

6.2 Protect the privacy of participants In order to protect the privacy of the children and adolescents in the test, when the research materials are provided to other organizations, the subject code or initials should be used instead of their ID number or real name. In addition, the researcher and the relevant staff involved in the research must keep the privacy information of the children and adolescents in the test confidential.

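### Section 5.2A compares the arms only with an unadjusted test picked by a normality pre-test; a pre-specified ANCOVA of change on baseline value and age has an expected cost of about 0.9% of variance and may gain precision

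*Combined protocol and SAP*

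**What the plan says.** Section 5.2A gives the only rule for comparing arms on continuous variables. It starts with a pre-test: "The normality test uses the Kolmogorov-Smirnov test". Then: "If the normal distribution is satisfied, the t test or one-way ANOVA is used"; and "if the normal distribution is not satisfied, the Mann-Whitney U test or the Kruskal Wallis test is used". No covariate is named, and no model that uses the visits jointly.

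Two other places mention the variables that one would adjust for. Section 5.2C lists "simple linear regression and stepwise multiple linear regression, using nonlinear regression if necessary", under the label of correlation analysis, with no treatment term and no fixed covariates. Section 5.4 says: "Subjects will be assigned to different subgroups for subgroup analysis based on age, gender, diopter, axial length, fundus structure, and functional changes". That splits the sample; it does not adjust the comparison of arms.

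The data for an adjusted analysis exist. Refraction and axial length are measured at baseline and at follow-up (Sections 3.4 and 4.2), and age is an entry criterion (Section 3.1.1). On visits, Section 4.1 says: "Combined use of 1% atropine and 0.01% atropine group is followed up after first week, then every three months"; and "0.01% atropine group is followed up every three months". Over the two years of treatment in Section 3.3, the arms share 24 / 3 = 8 quarterly visits. Only the combined arm has a week-1 visit.

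**The concern.** Two things are given up.

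- **The effect measure.** The pre-test settles, only after the data are in, whether the formal comparison is of means in D or mm or of ranks. Nothing prevents it from going one way at one visit and the other way at the next.
- **Precision.** Both arms are active, so the gap to be detected is probably small, and any variance explained by baseline or age is left in the error term.

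There is also a question about dropout. A test of the children who attend the analysed visit makes no use of the earlier visits of those who left. The trial is unmasked (Section 3), and Section 1.4 itself describes marked side effects and poor long-term compliance with 1% atropine. Dropout linked to progression is therefore conceivable, but no rate is given.

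**Working it through.** **Inputs from the documents.** 111 children per arm (Section 3.2); two-sided 5% (Section 5.3); two-year progression of 0.49 D on 0.01%, 1.20 D in controls, and a benefit of 0.92 D on 1% (Section 1.3).

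**Inputs assumed.** SD of two-year change 0.7 D (range 0.6 to 0.8); share of that variance explained by baseline and age together, R², 0 to 30%; change from baseline as the outcome, since Sections 1.3, 1.4 and 2 speak of progression. Section 3.2 gives no effect size, SD or power, so there is no figure of the plan's own to reproduce.

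**1. Gap used for illustration.** 0.49 − (1.20 − 0.92) = 0.21 D. This is an upper guide: it reflects two years of 1%, whereas here 1% is used for half a year, and Section 1.4 calls the two-year effects equal.

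**2. Precision and power.** SE = SD × √(1 − R²) × √(2/111); half-width = 1.96 × SE; power ≈ Φ(gap/SE − 1.96). With SD 0.7:

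| R² | SE (D) | 95% CI half-width (D) | Power at 0.21 D | Power at 0.10 D |
|---|---|---|---|---|
| 0 (unadjusted) | 0.094 | 0.184 | 61% | 19% |
| 10% | 0.089 | 0.175 | 65% | 20% |
| 20% | 0.084 | 0.165 | 70% | 22% |
| 30% | 0.079 | 0.154 | 76% | 25% |

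At a 0.21 D gap, SD 0.6 gives 74 to 88% over the same R² range, and SD 0.8 gives 50 to 65%.

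**3. Cost if both covariates are uninformative.** Expected variance factor with two covariates = (N − 3)/(N − 5).

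- N = 222: 219/217 = 1.009, a cost of 0.9%. Adjustment pays once R² exceeds 1 − 217/219 = 0.9%.
- 20% loss, N = 176: 173/171 = 1.012.
- 40% loss, N = 132: 129/127 = 1.016.
- These are expectations. By chance imbalance, a single trial of 222 can lose more (95th percentile 2.8%).
- In 40,000 simulated trials, type I error was 5.02% unadjusted and 5.06% adjusted.

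**4. Where a gain would come from.** Assume progression rates unrelated to baseline: slope SD 0.33 D/year (0.66 D over two years), visit noise 0.15 D, baseline SD 1.0 to 1.5 D. Variance of change = 0.66² + 2 × 0.15² = 0.4806, SD 0.693. Baseline then explains 0.15⁴ / [(baseline SD² + 0.15²) × 0.4806], which is 0.10% at SD 1.0 and 0.05% at SD 1.5. In this setting nearly all the gain must come from age.

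**5. How age enters a mixed model.** If age drives the rate of progression, its effect on change grows with time. In simulations of the step 4 model with age R² of 10 to 30%:

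- A mixed model with baseline-by-visit but one constant age term keeps 97 to 99% of the unadjusted variance at month 24. Power at 0.21 D is then about 62% at R² 30%, not 76%.
- ANCOVA keeps about 89 to 72%. The formula (1 − R²) × 219/217 gives 91 to 71%.

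The table in step 2 therefore applies to ANCOVA, or to a mixed model with age-by-visit.

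**6. Attenders only.** Take mean progression of 0.28 and 0.49 D, SD 0.7, and the same assumed rule in both arms: children progressing more than 1.20 D leave. Completers' mean = μ − 0.7 × φ(a)/Φ(a), with a = (1.20 − μ)/0.7.

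- μ = 0.28: a = 1.314, mean 0.150, loss 9%.
- μ = 0.49: a = 1.014, mean 0.292, loss 16%.

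The true 0.21 D gap shows as 0.14 D. Bias therefore does not require a dropout rule that differs between arms; it is enough that dropout depends on progression and the arms truly differ.

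**The case against.** The strongest reply is that this is an efficiency suggestion with an unknown return. The unadjusted test of change is valid with complete data, no document supplies an SD or a correlation, and the illustrated gain starts at zero. All of that stands. The case for the change rests on its low cost and on fixing the analysis in advance, not on a proven gain.

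A second reply is that the harm from the pre-test is limited, because Section 5.1A promises means and SDs for continuous variables whichever test is chosen. That is right: a difference in D or mm can still be derived. But the test that carries the conclusion still depends on the pre-test, and no confidence interval is promised.

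A third is that Section 5.2C already allows multiple regression. It does, but as a stepwise correlation analysis, so the covariates would be selected by the data and arm need not be in the model.

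A reader might go further and infer that dropout will bias the result. The documents do not support this: they give no dropout rate, so bias is a possibility and not a prediction. Nor can one say that the cost is at most 1%; that figure is an expectation with complete data.

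**Conclusion.** The point holds as a cheap improvement to the plan. Section 5.2A specifies no adjusted comparison of the arms and lets a pre-test choose the method. Replacing it with ANCOVA on baseline and age has an expected cost of 0.9% of variance at 222 children (1.2 to 1.6% with 20 to 40% loss) and pays once the two covariates explain about 1% of the variance of change.

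The possible gain, a half-width down to 0.154 D and power up to 76% at 0.21 D, rests on the assumed SD and R² and on a gap pieced together from Section 1.3. It could be nil. At a 0.10 D gap, power stays at 25% or less, so adjustment does not rescue the trial there.

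Two stronger readings are tempting. One is that the planned test is invalid; with complete data it is not. The other is that a repeated-measures model is better in any form; with a single constant age term it loses nearly all the gain from age at month 24.

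**What to change.** For spherical equivalent and axial length, replace the pre-test rule in Section 5.2A with:

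> Change from baseline at the primary time point will be compared between the arms by ANCOVA, with arm, baseline value of the outcome and age as terms. The adjusted mean difference will be reported with its 95% confidence interval. No normality test will decide the method. A Mann-Whitney test will be reported as a sensitivity analysis.

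If the sponsor wants the earlier visits of children who leave to count, a mixed model for repeated measures over the eight common quarterly visits can take the place of ANCOVA. It should include arm, visit, arm-by-visit, baseline-by-visit and age-by-visit, and omit week 1, which only one arm attends. An unstructured covariance over eight visits has 8 × 9 / 2 = 36 parameters, so a fallback structure should be named in advance. Such a model protects against dropout only as far as dropout depends on observed values.

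The wording needs a primary outcome, a primary time point and a rule for combining the two eyes. These are separate gaps and should be settled before follow-up data are examined.

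The cost is SAP wording, slightly more analysis work and the small expected loss of variance above. No new data, visits or children are needed.

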1.3 Studies about atropine for controlling myopia progression

In order to reduce the incidence of high myopia, many myopia control interventions have been carried out in children and adolescents at home and abroad. Among them, atropine, an M-receptor antagonist, has been shown to be effective in myopia control in many experimental and clinical trials in recent years. In ATOM2 study in Singapore, a randomized controlled clinical trial was conducted. Two years after the use of 1% atropine eye drops, children's myopia decreased by 0.92D and eye axis increased by 0.4mm compared with the control group. After 2 years of treatment with 0.5%, 0.1% and 0.01% respectively, the myopia of children increased by 0.30D, 0.38D and 0.49D, respectively, which were

significantly lower than that of the control group (1.20D). Although 1% atropine eye drops had myopic rebound effect after discontinuation, the rebound effect disappeared when the concentration of atropine was reduced to 0.1% and 0.01%.

In the LAMP study in Hong Kong, after one year of treatment with 0.05%, 0.025% and 0.01% respectively, the myopia of children increased by 0.27D, 0.46D and 0.59D, which were significantly lower than that of the control group (0.81D), and the ocular axis increased by 0.20mm, 0.29mm and 0.36mm, respectively, which were lower than that of the control group (0.41mm). Similar studies at home and abroad have also confirmed that the use of low-concentration atropine has a good effect on myopia control. At present, in Taiwan, Hong Kong, Singapore and other Chinese areas, children with high myopia risk and rapid growth of myopia have been more commonly treated with low-concentration atropine eye drops for intervention.

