The mechanism of atropine controlling myopia has not been fully elucidated. Early studies suggested that atropine could control myopia by regulating mechanism. However, McBrien found that atropine could still control the development of myopia after cutting off the regulating pathway through animal experiments. Therefore, the mainstream view is that atropine controls myopia by non-regulating mechanism. It may be through the antagonism of Mreceptor signaling pathway on the retina or scleral surface to slow down the development of myopia, but the specific mechanism has not yet been fully elucidated. Atropine eye drops belong to mydriasis and ciliary paralysis drugs. Long-term use of atropine eye drops can lead to symptoms such as dilatation of pupils, photophobia and blurring of close-range objects. These symptoms are closely related to drug concentration and frequency of use.

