1.4 The objectives of our study

From previous studies, investigators can find that 1% atropine has good effect in early myopia control, but its side effects are great, long-term use compliance is poor, and there is a rebound effect; 0.01% atropine has poor effect in early myopia control, and the effect of follow-up for one year is not as good as 0.05%, but the effect of follow-up for two years is equal to 1%, that is, long-term use effect is good, and there are few side effects. Considering that only 1% or 0.01% atropine eyedrops (gels) are available in atropine eyedrops approved by the drug administration, investigators consider whether 1% atropine can be used for six months, and 0.01% atropine for one and a half years to achieve better early myopia control, late consolidation efficacy and side effects. In addition, the current clinical studies mainly focus on diopter and ocular axis. This project will explore the changes of lens and fundus after atropine treatment, whether there are indicators that reflect the effect of atropine control earlier and more accurately than diopter and ocular axis, and explore the target of atropine for myopia control.

2. Research Objectives

To explore a better way to control myopia progression and eliminate adverse effects at the same time;

To provide reliably evidence for clinical guideline of atropine use in children;

To investigate the mechanism of atropine on eyes.

3.Trail Design

a randomized controlled, prospective cohort study, no mask.

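### Must Section 5.2C state how treatment arm enters its regressions, in case an early marker tracks progression only through arm?

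*Combined protocol and SAP*

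**What the plan says.** Section 5.2C, headed correlation analysis, consists of one line: "simple linear regression and stepwise multiple linear regression, using nonlinear regression if necessary". Nothing else in Sections 5.1 to 5.5 adds to it. Section 5.2A covers comparisons between groups, 5.4 lists subgroup factors (arm is not among them), and 5.5 says only that baseline and follow-up data are analysed and reported.

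The aim these regressions might serve is in Section 1.4. The project will "explore the changes of lens and fundus after atropine treatment" and ask "whether there are indicators that reflect the effect of atropine control earlier and more accurately than diopter and ocular axis". No section links that aim to a particular model.

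Section 3.2 randomises two groups of 111. Section 4.1 gives the combined arm a week-1 visit and three-monthly visits after that; for the control arm, "0.01% atropine group is followed up every three months". The first on-treatment visit common to both arms is therefore at three months.

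**The concern.** A simple regression over both arms has no arm term. A stepwise model may drop arm, or may never be offered it. If the 1% phase moves a marker and also slows progression, marker and progression will correlate in the pooled data even when they are unrelated among children on the same regimen. The marker would then show which regimen a child received, not how that child responded.

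The documents make both conditions plausible. Section 1.4 says that "0.01% atropine has poor effect in early myopia control", so an early difference in progression is what the design hopes to produce. Section 1.3, on pupil dilatation, light sensitivity and near blur, says: "These symptoms are closely related to drug concentration and frequency of use". Pupil size, accommodation and near acuity are measured every three months in both arms (Section 4.2.2). At stake is a misleading early indicator reported under the exploratory aims.

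**Working it through.** **Inputs.** 111 per arm, 222 in total (Section 3.2); two-sided 0.05 (Section 5.3). The documents give no SDs and no marker effects, so the standardised arm differences in marker (dM) and progression (dY) are assumed over a range. Association within each arm is set to zero. The plan has no figure of its own on this point to reproduce.

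**Correlation created by arm alone.** With equal arms,

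r = 0.25·dM·dY / √[(1 + 0.25·dM²)(1 + 0.25·dY²)].

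For dM = 1 and dY = 0.4: r = 0.1 / √(1.25 × 1.04) = 0.1 / 1.140 = 0.088.

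**False-positive rate.** With 220 degrees of freedom, λ = r·√[220/(1 − r²)], and the rate is about Φ(λ − 1.96) + Φ(−λ − 1.96). Here λ = 0.0877 × 14.83 / 0.996 = 1.31, so the rate is about Φ(−0.65) = 26%. Simulation agrees:

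| Marker shift (SD) | dY = 0 | dY = 0.2 | dY = 0.4 | dY = 0.6 |
|---|---|---|---|---|
| 0.25 | 5% | 5–6% | 7% | 8% |
| 0.5 | 5% | 6–7% | 11% | 18% |
| 1 | 5% | 10% | 26% | 49% |
| 2 | 5% | 18% | 55% | 87% |

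With arm in the model the rate is about 5% in every cell. If either shift is zero there is no artefact. Baseline predictors are unaffected, because randomisation balances them in expectation.

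**Which column applies?** Section 1.3 gives two gaps, and neither is this trial's contrast.

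- One-year Hong Kong trial ("the myopia of children increased by 0.27D, 0.46D and 0.59D" on 0.05%, 0.025% and 0.01%): 0.59 − 0.27 = 0.32 D. At an assumed SD of 1.0 to 0.5 D this is 0.32 to 0.64 SD.
- Two-year Singapore trial, 0.5% against 0.01%: 0.49 − 0.30 = 0.19 D, or 0.19 to 0.38 SD.

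For dM = 1, the first gap gives r = 0.071 to 0.136 and a pooled rate of about 18 to 53%. The second gives r = 0.042 to 0.083 and about 10 to 24%. For dM = 0.5, the second gives about 6 to 10%.

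**Which row applies?** Section 1.3 supports a regimen-related shift only for pupil and near-vision effects. It ties these to frequency of use as well as concentration. Under Section 3.3 the combined arm uses 1% daily for one week and then weekly, while the control arm doses daily. At three months frequency therefore works against concentration. Nothing in the documents shows a shift in lens or fundus markers, the tissues Section 1.4 names when it introduces the indicator aim.

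**Stepwise models with arm offered** (assumed entry P < 0.05, removal P > 0.10). One marker: 4–5%, 5–6%, 5–7% and 4–13% at shifts of 0.25, 0.5, 1 and 2 SD. Five markers, at least one falsely selected: 22–29% up to a 1 SD shift, against 21–23% when each of the five is tested singly with arm forced. That is mostly ordinary multiplicity. At 2 SD the five-marker rate is 19–46%.

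**The case for a change.** The best case for a change is that the omission is a fact, that 5.2C is the only listed method relating one measured variable to another, and that a between-arm test under 5.2A cannot show whether a child's marker change tracks that child's progression. If the regimen works as hoped, pupil size could appear to predict progression merely because it identifies the 1% arm. One sentence of SAP text would prevent this, with no new data. The stepwise results reassure only if arm is offered as a candidate, which the plan does not say.

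All of that stands as a conditional statement, and the arithmetic behind it is sound. It does not show that the plan commits to a faulty analysis. Pooling, the choice of outcome and the use of post-treatment markers as predictors are all inferred. The term false positive also presumes a question about individual children within a regimen. Section 1.4 asks for indicators that reflect atropine's effect, and for that question the difference between arms is itself informative. Other routes are open: 5.2A can show whether a marker separates the arms sooner than refraction or axial length does. Including arm also has a price when a marker is strongly shifted. The slope's standard error grows by √(1 + dM²/4), which is 3%, 12% and 41% at 0.5, 1 and 2 SD.

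**Conclusion.** No change is needed. Section 5.2C names regression families and leaves the models open. Unspecified handling of arm is one part of that gap, and an analyst can fill it sensibly, by including arm or by fitting within arms, without departing from the text. Week-1 markers exist only in the combined arm, so they cannot be pooled across arms at all.

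The risk is real only if simple regression, or a stepwise model not offered arm, is run on both arms together with an on-treatment marker, and regimen shifts both marker and progression. Under those assumptions the rate ranges from about 5% to 87% over the grid shown. The high figures need marker shifts of 1 to 2 SD, which the documents do not support for lens or fundus measures. These rates illustrate a mechanism; they are not estimates for this trial. The artefact is less likely at two years, where Section 1.4 regards 0.01% as matching 1%. The regimen comparison and analyses of baseline predictors are unaffected, so the point is confined to exploratory reporting.

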3.2 Groups and Sample size

Myopic children aged from 7-12 years old are randomly allocated into two groups: combined use of atropine sulfate 1% ophthalmic ointment and atropine sulfate 0.01% eye drop (experimental group) and atropine sulfate 0.01% eye drop (control group). Each group includes 111 participants.

3.3 Medications and usage:

3.3.1 control group: atropine sulfate 0.01% eye drop, once a day, once a drop, for two years;

3.3.2 Combined application group: atropine sulfate 1% ophthalmic ointment, once a day for the first week, once a drop for both eyes; and then once a week, once a drop for both eyes for half a year. Half a year later, atropine sulfate 0.01% eye drop is used once a day, one drop each time, with both eyes for one and a half years. Usage: Drop it into conjunctival sac, about the size of a rice grain, press the nasal root with thumb and index finger for 2 minutes after dripping, and use it before going to bed. Patients once a week are advised to use it before going to bed on Friday night.

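### With no primary outcome, time point or test order named, the two-sided 0.05 rule in 5.3 leaves the false-positive chance over refraction and axial length uncontrolled

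*Combined protocol and SAP*

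**What the plan says.** - **Decision rule.** Section 5.3: "All differences were statistically defined as $P < 0.05$ (bilateral". It is the only rule given for calling a result significant, and it covers all differences.
- **Multiplicity.** Section 5.2 mentions Bonferroni for pairwise comparisons between groups. Nothing is said about multiple outcomes, visits or subgroups.
- **Arms and size.** Section 3.2 has two randomised groups: "Each group includes 111 participants". No outcome, effect size, SD, power or dropout is attached to that number, so it does not point to a primary test either.
- **Visits.** Section 4.1: "0.01% atropine group is followed up every three months". The combined arm has the same schedule plus a week-1 visit. Section 4.2.2 lists refraction and axial length at every quarterly visit, and 3.3 sets two years of treatment.
- **Aims.** Section 2 includes "To provide reliably evidence for clinical guideline of atropine use in children". Section 1.4 describes the sequential regimen as a way "to achieve better early myopia control, late consolidation efficacy and side effects".
- **Further analyses.** Section 5.4 lists six subgroup bases. Section 5.5 allows follow-up data to be analysed and reported. Neither has an error rule.
- **Masking.** Section 3: "a randomized controlled, prospective cohort study, no mask".

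**The concern.** A trial meant to inform a guideline needs at least one claim whose false-positive rate is known. Here no test is marked as confirmatory, so P<0.05 on either measure, at whichever visit, could be presented as the trial's finding.

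The time point matters on the protocol's own account. Section 1.4 calls 0.01% atropine weak early on, yet says of it that "the effect of follow-up for two years is equal to 1"%. Section 3.3.2 moves the combined arm from 1% to 0.01% at six months. Results at month 6 and month 24 may therefore differ, and the plan does not say which one answers the question. Because treatment is unmasked and reports may be made during follow-up, a choice that is not dated in advance could be made, or appear to have been made, after seeing between-arm data.

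**Working it through.** **Inputs from the document.** Two-sided 0.05 per test (5.3); two arms of 111 (3.2); visits every 3 months (4.1) over 24 months (3.3); SE and AL both measured at each visit (4.2.2).

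**Assumed, because the document gives none.** The SE-AL correlation of the test statistics is 0.6-0.8, with signs set so that positive favours the combined arm. Visit correlations are as in the table below. Each test uses one value per child and is valid at its nominal level. There is no true effect at the tested visits.

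**1. The plan's own figure.** 2 × (1 − Φ(1.960)) = 0.050, or 0.025 in each direction. It reproduces as a per-test level.

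**2. What Bonferroni corrects.** With k groups there are k(k−1)/2 pairs. For k = 2 this is 1, so the adjusted level is 0.05/1 = 0.05: no change.

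**3. Number of tests.** 24/3 = 8 shared visits; 2 measures × 8 visits = 16.

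**4. Both measures at one visit.** P(at least one) = 1 − P(|Z1| ≤ 1.96 and |Z2| ≤ 1.96), with Z1, Z2 bivariate normal. P(in favour) = 1 − P(Z1 ≤ 1.96 and Z2 ≤ 1.96).

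| SE-AL correlation | At least one | In favour |
|---|---|---|
| 0.6 | 8.8% | 4.4% |
| 0.7 | 8.3% | 4.2% |
| 0.8 | 7.8% | 3.9% |

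Under independence the first figure would be 1 − 0.95² = 9.75%.

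**5. Both measures, any of 8 visits.** Simulated as a 16-variate normal (SE-AL correlation combined with visit correlation), 1,000,000 null replicates per setting.

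| Visit correlation | SE-AL 0.8 | SE-AL 0.6 | In favour |
|---|---|---|---|
| Equal, 0.95 | 14% | 16% | 7-8% |
| Equal, 0.9 | 18% | 20% | 9-10% |
| AR(1), 0.95 | 19% | 21% | 9-10% |
| Independent increments | 26% | 29% | 13-15% |
| Equal, 0.7 | 28% | 31% | 14-16% |
| AR(1), 0.8 | 31% | 35% | 16-18% |
| Equal, 0.5 | 36% | 40% | 18-20% |
| AR(1), 0.6 | 40% | 44% | 21-23% |

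The middle five rows give 18-35%; all rows give 14-44%.

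**6. Less extreme uses of the rule.** Both measures at months 12 and 24 only, over the settings of the middle five rows: 11-16% (5-8% in favour). If a real effect exists at months 3-6 and has gone by month 9, only months 9-24 can give false positives: 16-28% (8-14% in favour) in those settings.

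**7. A fixed sequence.** If the second measure is tested only after the first succeeds, then under no effect P(at least one false positive) = P(first test rejects) = 0.05.

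**8. Detectable difference at 80% power.** (1.960 + 0.842) × √(2/111) = 0.376 SD with no dropout. With an assumed 20% dropout, 111 × 0.8 ≈ 89 per arm and 2.802 × √(2/89) = 0.420 SD. Splitting alpha equally (0.025 per measure) gives (2.241 + 0.842) × √(2/111) = 0.414 SD with no dropout.

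**The case against.** **A level of 0.05 is conventional, and the plan claims no familywise control.** This stands. The number 0.05 is not the defect; the defect is that no test is designated to carry it. Nor can one say without condition that 0.05 is right per test. Both eyes are measured and no rule says which eye, or what average, is analysed. A reader might infer that eyes will be pooled as independent, which would put the per-test level at about 13-16% for an assumed inter-eye correlation r of 0.7-0.9, from 2 × (1 − Φ(1.96/√(1+r))). The document does not say this, so the figures here are conditional on one value per child.

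**Nobody would claim success on any of 16 tests.** Perhaps not. The any-visit rule is not in the plan; it is only not excluded. The one-visit figure needs fewest assumptions, and it is a modest inflation.

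**A true early effect is expected, so a null at all visits is unrealistic.** This is fair. Step 6 shows the later visits still carry a risk, though that case itself assumes that the early difference has vanished by month 9.

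**Two of the three objectives are worded as exploration or investigation.** This too stands: for the mechanism aim the gap matters much less. The seriousness rests on the guideline objective.

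**The rebound statement proves that the visit decides the conclusion.** A reader might infer this from section 1.3 ("Although 1% atropine eye drops had myopic rebound effect after discontinuation"), but it goes too far. That sentence concerns stopping 1%, whereas here the combined arm changes to 0.01%. The documents support only that month 6 and month 24 may differ.

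**Conclusion.** The concern holds and should be corrected before any between-arm result is claimed. No primary outcome, time point or test order is named in the document supplied, and its one multiplicity method has nothing to adjust in a two-arm comparison.

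The firmest measure of size is the single visit with two measures: about 8-9% instead of 5%, or about 4% instead of 2.5% in favour of the combined arm. It rests on an SE-AL correlation of 0.6-0.8 and valid tests on one value per child.

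A reader might take 18-35%, or the upper end of 14-44%, as this trial's error rate. The documents do not support that. Those values need an any-visit claim rule that the plan does not state, no true effect at any visit, and correlations that the plan does not give. They show how far the rate can move when nothing is fixed, and are neither an estimate nor a bound. Nor do the documents suggest that the sponsor intends to select a favourable visit.

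**What to change.** **In 5.3**, name one confirmatory test at two-sided 0.05: the between-arm difference in change from baseline in AL or in cycloplegic SE (the sponsor's choice) at month 24, the end of the two-year regimen, or at another single time point that the sponsor justifies. To make it one test, also state:

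- one value per child (a prespecified eye, or the mean of both eyes);
- the refraction method, if SE is chosen, since 4.2.2 lists both autorefraction and subjective refraction;
- one prespecified test, not selected by the Kolmogorov-Smirnov pretest in 5.2.

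Date the choice before any between-arm summary is produced, and say so if one already exists. Test the other measure second, in fixed sequence at the same time point; an alpha split is an acceptable alternative. List early control and side effects as named secondary outcomes. Report these and all other visits, outcomes and subgroups as estimates with 95% confidence intervals and no confirmatory claim. If a primary outcome is already recorded elsewhere, carry it into 5.3.

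**In 5.5**, state that between-arm reports before the primary time point are descriptive.

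**In 3.2**, add a line giving the detectable difference for the named outcome (about 0.38 SD with no dropout, 0.42 SD at 20%).

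**Cost.** Wording only, with no extra children or visits. A fixed sequence takes no power from the first test; an equal alpha split raises the detectable difference from 0.38 to 0.41 SD. The downsides are that results at other visits and on other outcomes can no longer be called confirmatory, and that under a fixed sequence the second measure can be claimed only if the first succeeds.
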